# 9.3 Muscle Strength Test Schedule

Table 9: Muscle Strength Testing Schedule

	6 mos - 3 yrs	3 - 4.9 yrs	5 - Non-Ambulant		
Bayley IV					
Time to climb four					
stairs					
NSAA					
100 meter					
MVICT*					
PFTs					
Number of	1	2	_		
Assessments	1	3	5		

\*The lowest age at which the MVICT will be administered will be based on the Clinical Evaluators' discretion in ability to cooperate.

# 9.4 Long Term Follow up

We will follow the most recent FDA guidelines with regard to long-term subject follow-up following gene transfer. As discussed and based on prior experiences with rAAV or transgene, there is a very low probability of gene transfer-related adverse events. We will, however, evaluate short-term safety over a two-year period that incorporates the active phase of the protocol. Subjects will then transfer to an annual monitoring program where data will be collected from annual standard of care visits for up to 5 years.

If newly identified risks are associated with our product, or if the subjects suffer any adverse events during this period, we will initiate a long-term follow-up according to the FDA guidelines. We will, of course, notify CBER if there is any indication of need to extend follow-up period. All subjects will be provided with written instructions on how to contact the Sponsor Investigator or study coordinator if they experience any serious adverse event that they consider possibly related to study treatment or study participation. This information will also be included in the Informed Consent document. All subjects will be instructed to notify the Sponsor Investigator of a change of address or contact information.

The final results of the clinical trial will be shared with the participants at the completion of the study when all data has been collected, analyzed, and published. However, if significant findings become available that might increase the risk of the subjects or might affect their decision to remain in the study, then information will be made available as soon as it is available.

At the time of death, no matter the cause, permission for an autopsy will be requested of their families. Subjects will be asked to advise their families of this request and of its scientific and medical importance.

## 10 PROCEDURE CRITERIA

# 10.1 Muscle biopsy

The baseline open muscle biopsy will be performed in one quadriceps muscle, or other appropriate muscle as determined by the SI. Another open muscle biopsy of the quadriceps, or other muscle as determined by the SI (biopsy will be in the contralateral leg to the pre-treatment biopsy, unless otherwise determined by the SI), will be performed 3 months post-infusion.

All open muscle biopsies will be performed under anesthesia, as per NCH standard clinical protocols.

Needle muscle biopsies of the quadriceps muscles (using the Vacora device; C.R. Bard, Inc.) will be performed at 6 and 12 months. In order to avoid resampling of the previous biopsy site, the open biopsies are anticipated to be performed in the vastus lateralis muscles, and the needle biopsies in the vastus medialis muscles. Every effort will be made to sample these same muscles in all subjects; however, in subjects (particularly older ambulant subjects) with limited quadriceps musculature, alternate muscle biopsy sites may be selected at the SI's discretion (including biceps, gastrocnemius, tibialis anterior or deltoid muscles).

# 10.2 Magnetic Resonance Imaging (MRI)

In order to avoid the risk of sedation for an exploratory efficacy measure, muscle MRI will **not** be performed in any subjects who are unable to remain still for a MRI without sedation. To evaluate if a subject will be able to remain still, a mock-MRI will be performed in coordination with Child Life during the screening visit. If the mock-MRI is unable to be completed, the subject will not be required to provide a clinical MRI during the trial. If the MRI is unable to be performed without sedation, it will not be recorded as a protocol deviation.

# 10.3 Pulmonary functional tests (PFTs)

PFT testing will be performed in subjects 5 years or older. If the subject is too young to reliably test these values, it will not be performed and will not be recorded as a protocol deviation.

# 10.4 Vector Shedding Studies

Vector shedding analysis post dosing will be performed on DNA isolated from different biological fluids (plasma, urine, saliva and feces) until three consecutive samples are negative for the presence of viral DNA for each specimen type.

# 10.5 Height Measurements

Height will be measured with the patient standing when ambulatory. If the patient is non-ambulatory, ulna length measurement will be used to calculate height.

#### 10.6 Concomitant Medications

Prior and concomitant medications will be captured in the eCRF form two weeks prior to study enrollment through the last study visit. The SI will encourage participants to maintain the medication and supplements they are on at enrollment through the course of the study. Subjects on aspirin or drugs that could affect coagulation will continue their medication as indicated.

Several investigations show that preoperative aspirin ingestion and intravenous heparin therapy can be administered safely without concerns about the risk of postoperative bleeding and should not lead to modification or cessation of such therapy. Use 4 years old or greater must already be on a stable dose of prednisone, prednisolone, or deflazacort for 12 weeks at time of enrollment as part of the inclusion criteria.

# 10.6.1 Prophylactic Administration of Prednisone/Prednisolone

All subjects will be discharged from the hospital on oral prednisone or prednisolone at 1 mg/kg/day, which will be adjusted according to IFN-gamma T-cell studies in the following weeks. Subjects will also continue on a PPI until they return to their baseline corticosteroid dose or sooner based on the subject's symptoms and discretion of the sponsor investigator and/or parent.

If the **30 day** post-infusion IFN-gamma T-cell responses to AAV9 and dystrophin show ≤50 SFC per 1 x 10^6 PBMCs, the subject's prednisone or prednisolone dose will be decreased back to the standard clinical dose of 0.75 mg/kg/day. Those subjects who had been on deflazacort may be switched back to the standard clinical dose of 0.9 mg/kg day. For either regimen, approximations of these target doses may be allowed to account for pill formulations (for prednisone and deflazacort), as in clinical practice. If either the AST or ALT exceeds >2.5X the subject's baseline values, and results are confirmed on a follow-up blood test, the prednisone or prednisolone regimen will be maintained at 1 mg/kg/day until the enzyme levels fall within a range, 2.5X the baseline value. Subjects may be asked to undergo a weekly blood test outside of prescheduled visits should the SI deem it necessary to monitor the T-cell response or AST/ALT levels more closely.

If the IFN-gamma T-cell responses show  $\geq 50$  SFC per 1 x  $10^6$  PBMCs, we may increase the dose to approximately 2 mg/kg/day depending on T-cell response measured by ELISpot assay and prolong a subsequent tapering protocol based on the individual subject's immune response profile as assessed by subsequent ELISpot assays (as on the schedule above). Based upon other studies performed at NCH, we anticipate that oral prednisone or prednisolone may be administered for up to 120 days post gene transfer prior to the return to the standard clinical corticosteroid regimen of each subject.

#### 11 ASSESSMENT OF SAFETY

The primary outcome for this clinical trial is safety.

## 11.1 Adverse and Serious Adverse Event

## 11.1.1 Definition of an Adverse Event

As stated above this protocol will follow the final regulations issued by the Food and Drug Administration addressing the safety reporting requirements for investigational new drug applications (INDs) found in 21 CFR part 312 and for bioavailability and bioequivalence studies found in 21 CFR part 320. "Safety Reporting Requirements for INDs and BA/BE Studies".

 $\frac{http://www.fda.gov/downloads/Drugs/GuidanceComplianceRegulatoryInformation/Guidances/UCM227351.pdf}{CM227351.pdf}$ 

**Adverse Event (AE)**: Adverse event means any untoward medical occurrence associated with the use of a drug in humans, whether or not considered drug related.

Adverse events will be graded by the investigator accordingly (as indicated in Section 11.4):

- 1 = mild
- 2 = moderate
- 3 = severe
- 4 =life threatening or debilitating
- 5 = fatal

Association or relatedness to the study agent will be graded as follows:

- 5 = unrelated
- 4 = unlikely
- 3 = possibly
- 2 = probably
- 1 = definitely related.

**Adverse reaction:** An adverse reaction means any adverse event caused by a drug. Adverse reactions are a subset of all suspected adverse reactions for which there is reason to conclude that the drug caused the event.

Suspected adverse reaction (21 CFR 312.32(a)) Suspected adverse reaction (SAR) means any adverse event for which there is a reasonable possibility that the drug caused the adverse event. For the purposes of IND safety reporting, 'reasonable possibility' means there is evidence to suggest a causal relationship between the drug and the adverse event. A suspected adverse reaction implies a lesser degree of certainty about causality than adverse reaction, which means any adverse event caused by a drug.

#### 11.1.2 Unexpected Adverse Events

Unexpected adverse events are those which are not previously reported with recombinant AAV vectors, commonly not seen in association with the subject's underlying disease or with the procedures to be used in this study, or are related to a known toxicity but differ because of greater severity or specificity.

Potential expected AEs include localized injection site reactions, which might also be related to the procedure and be independent of the AAV vector itself. Asymptomatic elevations in transaminases are a feature of Duchenne muscular dystrophy, as they are related to release of AST and ALT from muscle tissue and correlate with levels of creatine kinase. These are a feature of the disease itself. Levels of AST (up to 12.3X the upper limit of normal) and ALT (up to 22.6X the upper limit of normal) are expected to be seen at baseline, and in the setting of normal GGT function are not indicative of muscle injury. They are thus not exclusionary for enrollment and will not be recorded as adverse events prior to gene transfer.

Systemic delivery of AAV vectors have resulted in AEs including asymptomatic transient transaminitis (up to levels of 2.5x the subject's baseline value and 3X the upper limit of normal for DMD subjects for AST and ALT) with preserved liver synthetic function and no significant elevation in GGT) following gene transfer (see Section 11.4.2).

#### 11.1.3 Serious adverse event (SAE)

An adverse event or suspected adverse reaction is considered "serious" if, in the view of the investigator/sponsor, it results in any of the following outcomes: Death, a life-threatening adverse event, inpatient hospitalization or prolongation of existing hospitalization, a persistent or significant incapacity or substantial disruption of the ability to conduct normal life functions, or a congenital anomaly/birth defect. Important medical events that may not result in death, be life-threatening, or require hospitalization may be considered serious when, based upon appropriate medical judgment, they may jeopardize the patient or subject and may require medical or surgical intervention to prevent one of the outcomes listed in this definition. Examples of such medical events include allergic bronchospasm requiring intensive treatment in an emergency room or at home, blood dyscrasias or convulsions that do not result in inpatient hospitalization, or the development of drug dependency or drug abuse.

To reiterate, an SAE is an event in categories 3, 4, and 5.

**Category 3:** Severe adverse event; inability to carry on normal activities; required professional medical attention

**Category 4**: Life-threatening or permanently disabling adverse event

**Category 5:** Fatal adverse event

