Subjects will be closely monitored for side effects during the infusion, including continuous heart rate, respiratory rate, and pulse oximetry; and intermittent blood pressure monitoring. Heart rate, respiratory rate, pulse oximetry (only if sedation is being utilized), temperature, and blood pressure will be measured before and immediately after the infusion, and at least every five minutes during the infusion if sedated, and every 15 minutes if not sedated. Monitoring will be repeated at 15 minutes post-infusion, every 15 minutes for 4 hours following the infusion, and then every hour until transfer from the PICU to the Neurology floor. On the Neurology floor, vital signs will be measured every 4 hours until discharge.

Infusion reactions: Infusion will be terminated for evidence of an allergic reaction of **grade 2 or greater**, including anaphylaxis, based upon CTCAE v5.0 criteria, and reported using these criteria:

Grade 1: Transient flushing or rash, drug fever <38° C (<100.4° F); intervention not indicated

Grade 2: Rash, flushing, urticaria, dyspnea, drug fever >38° C: Intervention or infusion interruption indicated; responds promptly to symptomatic treatment (e.g., antihistamines, NSAIDS, narcotics); prophylactic medications indicated for ≤24 hrs

Grade 3: Prolonged (e.g., not rapidly responsive to symptomatic medication and/or brief interruption of infusion); recurrence of symptoms following initial improvement; hospitalization indicated for clinical sequelae (e.g., renal impairment, pulmonary infiltrates)

Grade 4: Life-threatening consequences; urgent intervention indicated

Grade 5: Death

Under CTCAE v5.0 criteria, anaphylaxis is by definition grade 3 (Symptomatic bronchospasm with or without urticaria; allergy-related edema/angioedema, hypotension), and would result in infusion termination and systemic treatment.

Subjects will remain in an independent hospital room following gene transfer and remain hospitalized for up to 48 hours post gene transfer.

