# 11.3.2 Safety Reporting

The investigator or his designee will report all serious and unexpected adverse events to the IRB, CBER/FDA and DSMB according to regulatory requirements described as follows:

- **IRB**: All Serious Adverse Events (SAEs) and Dose Limiting Toxicities (DLTs), regardless of expectedness, relatedness, or if they meet the definition for unexpected problems in the clinical trial will be reported to the **IRB** as soon as possible, but not later than **15 calendar days** after the sponsor's initial receipt of the information.
- **DSMB**: All Serious Adverse Events (SAEs) and Dose Limiting Toxicities (DLTs) that are lifethreatening will be reported to the **DSMB** within 48 hours of notification, regardless of expectedness, relatedness, or if they meet the definition for unexpected problems to the clinical trial.
- **FDA:** Any serious adverse event that is fatal or life-threatening, that is unexpected, and associated with the use of the gene transfer product will be reported by the study investigator to the **FDA** as soon as possible, but not later than **7 calendar days** after the sponsor's initial receipt of the information.

Serious adverse events that are unexpected and associated with the use of the gene transfer product, but are not fatal or life-threatening, will be reported to the **FDA** as soon as possible, but not later than 15 calendar days after the sponsor's initial receipt of the information.

Changes in this schedule will be permitted only where, under the **FDA IND** regulations [21 CFR 312(c) (3)], changes in this reporting schedule have been approved by the FDA and are reflected in the protocol.

If, after further evaluation, an adverse event initially considered not to be associated with the use of the gene transfer product is subsequently determined to be associated, then the event will be

reported to the **FDA** as soon as possible, but in no case later than **15 calendar** days after the determination is made.

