Relevant additional clinical and laboratory data will become available following the initial serious adverse event report. Relevant follow-up information to an IND safety report will be submitted concurrently to the **FDA/IRB and the DSMB** as soon as the information is available and will be identified as such, i.e., "Follow-up IND Safety Report." If a serious adverse event occurs after the end of a clinical trial and is determined to be associated with the use of the gene transfer product, that event will be reported concurrently to the **FDA** within 15 calendar days of the determination.

Any finding from tests in laboratory animals that suggests a significant risk for human research participants including reports of mutagenicity, teratogenicity, or carcinogenicity will be reported to **FDA** and the **DSMB** as soon as possible, but not later than 15 calendar days after the sponsor's initial receipt of the information.

Should a serious adverse event deemed possibly, probably or definitely related to the study agent occur during administration, the study agent will be discontinued, appropriate treatment will be given under medical supervision and the subject will be examined as frequently as necessary thereafter until symptoms cease or stabilize.

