# 11.4 Dose limiting toxicity (DLT)

Dose limiting toxicity is defined as any adverse event that is possibly, probably, or definitely related to the study agent, and is unexpected. This would include any grade 3 event, according to the Common Terminology Criteria for Adverse Events (CTCAE) version 5.0; these classifications are outlined in **Table 10**.

Note: Elevations in transaminases and transient alterations in WBCs, as outlined in Section 12.4.2, above, are expected, and will not be considered as dose limiting when within the ranges noted therein.

Table 10: Adverse Event Classification

1	Mild adverse event; did not require treatment
2	Moderate adverse event; resolved with treatment
3	Severe adverse event; inability to carry on normal activities; required professional
	medical attention
4	Life-threatening or permanently disabling adverse event
5	Fatal adverse event

Study enrollment will be halted by the investigators when any subject experiences two or more **Grade 3**, **or higher** adverse event toxicity that are unexpected and **possibly**, **probably**, **or definitely related** to the study drug. The event will then be reviewed by the Data Safety Monitoring Board (DSMB) before making a determination to continue enrollment as described in Section 0.

Laboratory tests with values within the clinically significant range will be repeated during the same visit whenever possible (refer to CTCAE v5.0 for a complete list of clinically significant range values). If the test result returns after the subject leaves the clinic, they will be immediately contacted. For local residents they will be asked to return to the outpatient clinic for a repeat test. For non-local residents, arrangements will be made to have the blood test redrawn in a laboratory close to home or by their primary care physician. To avoid any confusion for the primary care physician, they will be informed (with permission from the subject) of their participation in the study at the time of gene transfer. If the AE requires treatment, this will be carried out by the primary care physician or a doctor of choice selected by the subject. We will obtain copies of repeat laboratory tests and any relevant medical records that will be added to the subject's research chart.

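### Section 11.1.3 defines a serious adverse event by outcome and then restates it as any category 3 to 5 event; the two are not equivalent, and nothing says which prevails

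*Combined protocol and SAP*

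**What the plan says.** Section 11.1.3 lists the outcomes that make an event serious: death, threat to life, "inpatient hospitalization or prolongation of existing hospitalization", lasting or significant incapacity or substantial disruption of normal functioning, and birth defect. It adds important medical events, by judgment. No severity grade is required.

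The section then says "To reiterate, an SAE is an event in categories 3, 4, and 5" and prints the three categories. They match Table 10 in Section 11.4, where category 2 reads "Moderate adverse event; resolved with treatment". Category 3 is a severe event, described by inability to carry on normal activities and a need for professional care.

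Section 11.3.2 uses the SAE label in several rules:
- SAEs and dose-limiting toxicities (DLTs) go to the IRB within 15 calendar days, "regardless of expectedness, relatedness, or if they meet the definition for unexpected problems in the clinical trial".
- The 15-day FDA report covers "Serious adverse events that are unexpected and associated with the use of the gene transfer product, but are not fatal or life-threatening".
- "Should a serious adverse event deemed possibly, probably or definitely related to the study agent occur during administration, the study agent will be discontinued".

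Section 11.4.1 exempts events due to disease progression from the expedited reports. Section 12.1.3 gives the DSMB a listing of SAEs, and Section 17.3.1 puts summaries of SAEs in the annual report.

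**The concern.** Seriousness and severity are different attributes of an event, but the closing sentence of 11.1.3 presents the second as a repetition of the first. Two careful people could classify the same event differently, each following the protocol. Safety is the primary outcome and at most 3 subjects will be dosed, so each event will be read individually. At stake is whether some events reach the IRB within 15 days, whether they appear as SAEs in the DSMB and annual reports, and in a narrow case whether an infusion is discontinued.

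**Working it through.** There is no figure to reproduce and no arithmetic applies. The check compares the two definitions case by case, then traces each rule to its trigger.

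**Step 1: where the definitions differ.**
- *Categories 4 and 5.* Life-threatening, permanently disabling and fatal events are SAEs under both.
- *Gap 1, serious by outcome only.* A category 1 or 2 event that causes or prolongs admission, or is judged an important medical event. Table 10 does not rule out admission in category 2. One example follows from Section 10.1: "All open muscle biopsies will be performed under anesthesia, as per NCH standard clinical protocols". Vomiting after the 3-month biopsy that settles with treatment but leads to an unplanned overnight stay is category 2 and serious by outcome. It is due to the procedure, so it is neither a DLT nor disease progression. A second example is gastrointestinal upset from the raised steroid dose, foreseen in 9.1.2.1, that prolongs the stay after infusion.
- *Gap 2, serious by category only.* A category 3 event with no listed outcome and not judged an important medical event. This set is small on the printed wording, because inability to carry on normal activities overlaps heavily with substantial disruption of normal functioning. An asymptomatic laboratory value falls here only if CTCAE grading, which Section 11.4 links to Table 10, sets the category.
- *Sensitivity to wording.* If the need for professional care alone made an event category 3, gap 1 would shrink and gap 2 would widen to every event that needed a clinician.

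**Step 2: which rules depend on the sentence followed.**
- *DSMB SAE listing (12.1.3) and annual SAE summaries (17.3.1):* yes. Both use the label.
- *15-day IRB report (11.3.2):* yes, for events that are neither DLTs (reported anyway) nor disease progression (exempt). These are mainly expected or unrelated events.
- *Discontinuation during administration (11.3.2):* yes, for non-allergic related events in either gap. Allergic reactions have their own rule in 9.1.2.2: "Infusion will be terminated for evidence of an allergic reaction of" grade 2 or worse.
- *15-day FDA report (11.3.2):* possibly. It is worded by SAE status, but the regulatory commitments in 11.1.1, 11.3.1 and 11.4 may settle it in practice.
- *48-hour DSMB report and 7-day FDA report (11.3.2):* no. The first is limited to life-threatening events and the second to fatal or life-threatening ones.
- *Enrollment halt (6.5, 11.4, 11.5):* no. It uses grade, expectedness and relatedness.

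Other uses of the label, such as the DSMB timeline in 12.1.3 and the monitor's check in 15.1, inherit the same ambiguity.

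**Step 3: the DLT definition.** Section 11.4 can be read as covering unexpected related events of any grade, or of Grade 3 and above. On the first reading all such events reach the IRB whatever their label. On the second, unexpected related category 1 or 2 events with a serious outcome also depend on the label. The conclusion holds on both.

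**The case against.** The strongest reply is that the two sentences can be read together. The first says an event is serious if it has a listed outcome, not only if, so the second may simply add categories 3 to 5. With the commitments to FDA safety regulations in 11.1.1 and 11.3.1, an investigator would be unlikely to drop an admitted event because it was category 2. This is a sensible way to run the trial, but it is not what is written: the sentence claims to repeat the definition and says what an SAE is, not what it also includes. The IND safety report in 11.3.1 covers only unexpected and associated SAEs, while the IRB rule is wider.

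A second reply is that admission points to category 3 anyway. The allergic-reaction scale in 9.1.2.2 places hospitalization for clinical sequelae in Grade 3. That makes gap 1 smaller in practice, but Table 10 contains no such rule for other events.

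A third reply is that oversight is hardly affected, and much of it stands. The DSMB also receives all adverse event details and a summary by severity, so its SAE listing changes in label and not in what it can see. Section 11.5 requires consultation with the DSMB on every related Grade 3 or higher event.

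A reader might infer that the conflict weakens the stopping rule, hides events from the DSMB or means that FDA reports will be missed. The documents do not support any of these. The halt does not use the label, the DSMB sees all adverse events, and the FDA effect is only possible.

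**Conclusion.** The point holds. The two definitions are not equivalent, they differ in both directions below category 4, and no text ranks them. If the category sentence is followed, an admitted or medically important category 1 or 2 event that is expected or unrelated, and not due to disease progression, loses its 15-day IRB report. It also loses its place in the DSMB SAE listing and the annual SAE summaries. That gap matters most for safety; the category 3 gap is smaller.

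The size is a matter of reach, not frequency. Without event rates, and with 1 to 3 subjects planned, the number of affected events cannot be computed and is probably small. The conclusion assumes that category 2 can include an admitted event, which Table 10 allows. It does not rest on the laboratory example or on either reading of the DLT definition. This is a safety-reporting definition that should be corrected; no efficacy estimate or test changes.

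**What to change.** In 11.1.3, make the outcome definition govern. Replace the closing sentence with: *In addition, any category 3, 4 or 5 event will be handled as an SAE for the reporting and discontinuation rules in Section 11.3.2, whether or not it meets an outcome above; the 11.4.1 exemption is unchanged.* Record seriousness and severity as separate eCRF fields, if this is not already done; the eCRF is not in the documents.

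Deleting the category sentence alone would be simpler, but it would take category 3 events without a serious outcome out of the 15-day FDA wording. With the added sentence, no IRB report, FDA report or infusion stop is lost.

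The cost is one sentence in 11.1.3 and a check of the eCRF. The small downside is that some category 3 events without a serious outcome continue to be reported as SAEs.
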